#### 2.4.3 Primary Efficacy Analysis

The Month 1 responder rates of abobotulinumtoxinA will be compared with placebo

#### 2.4.4 Secondary Analysis

## 2.5 Safety Analysis

All safety data will be summarized descriptively by treatment group based on the safety population using the Observed Cases (OC). There are no planned inferential statistical analyses of safety endpoints.

### 2.5.1 Extent of Exposure

Because subjects will receive a single dose of investigational product, no summary of extent of exposure will be performed. Extent of exposure will be provided in a subject data listing.

### 2.5.2 Adverse Events

An overall summary of all AEs will be provided by treatment group, which will include:

- number and percentage of subjects with at least one AE and number of events,
- number and percentage of subjects with at least one TEAE and number of events,
- number and percentage of subjects with at least one treatment-related TEAE and number of events,
- number and percentage of subjects with at least one mild, moderate, and severe TEAE and number of events,
- number and percentage of subjects with at least one TEAE leading to discontinuation and number of events,
- number and percentage of subjects with at least one serious TEAE and number of events.

All TEAEs, serious TEAEs, TEAEs by maximum intensity, TEAEs by causality, TEAEs by maximum intensity and causality, treatment-related TEAEs, and TEAEs leading to discontinuation will be summarized by treatment group, SOC, and PT including number of subjects with at least one event, percentages, and number of events.

For treatment-related AEs, the number of days to onset and duration of event will be summarized by treatment group, SOC, and PT.

Time to onset of an AE will be derived as the start date minus the date of treatment. If the start date is missing, it will be assumed that the AE started on the day of treatment.

Duration of an AE will be derived as the stop date minus the start date + 1. If the start date is missing, it will be assumed that the AE started on the day of treatment. Missing stop date will not be imputed and therefore no duration will be calculated in these cases.

For subject counts, a subject will only be counted once per SOC and once per PT in cases where multiple events are reported for a subject within SOC or PT. For event counts, subjects with multiple events in a category will be counted for each event.

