9.1.3.1 Safety Analysis

A summary of all AEs will be provided, which will include:

- number of subjects who did not have an AE
- number of subjects with at least one AE and number of events
- number of subjects with at least one TEAE and number of events
- number of subjects with at least one related TEAE and number of events
- number of subjects with at least one TEAE by causality
- number of subjects with at least one TEAE by maximum intensity
- number of subjects with at least one TEAE leading to discontinuation
- number of subjects with at least one serious TEAE.

All TEAEs, treatment emergent SAEs, TEAEs by maximum intensity, TEAEs by causality, TEAEs by maximum intensity and causality, and TEAEs leading to discontinuation will be summarized by SOC and PT including number of subjects with at least one event, percentages, and number of events. All related TEAEs will also be summarized by time to onset and duration.

Data for hematology, blood chemistry, antibodies, and vital signs will be summarized by descriptive statistics with the value at each visit as well as the change from baseline. Shift tables for out of normal ranges results will be presented for hematology, blood chemistry and antibodies. The numbers and percentages of subjects with abnormalities in physical examination and vital signs will also be summarized. The results of the urine pregnancy tests will be listed.

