### (i) Treatment Emergent Adverse Events (TEAEs)

Adverse events (AEs) are to be monitored throughout the course of the study. The study period for the purpose of AE collection is defined as the period from the signing of a study specific informed consent to study exit for a subject. AEs recorded on the electronic case report forms (eCRFs) will be coded using the Medical Dictionary for Regulatory Activities (MedDRA). AEs will be classified as treatment-emergent adverse events (TEAEs) if the AE had an onset time greater than or equal to the time of the dose of study treatment.

Adverse events endpoints include:

- Incidence,
- Causality (related/not related to investigational product),
- Intensity (mild/moderate/severe),
- Time to onset,
- Duration,
- Leading to study withdrawal,
- Seriousness.

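### Setting a missing adverse event start date to the day of treatment distorts time to onset and duration for treatment-related events

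*SAP*

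**What the plan says.** SAP 2.5.2 gives two derivations. The first is "Time to onset of an AE will be derived as the start date minus the date of treatment". The second is "Duration of an AE will be derived as the stop date minus the start date + 1". Each is followed by the same imputation: "If the start date is missing, it will be assumed that the AE started on the day of treatment". The visible text attaches no condition to it. A missing stop date is handled the other way: "Missing stop date will not be imputed and therefore no duration will be calculated in these cases".

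The scope of the two summaries is limited to related events. The SAP says "For treatment-related AEs, the number of days to onset and duration of event will be summarized by treatment group, SOC, and PT", and Protocol 9.1.3.1 says "All related TEAEs will also be summarized by time to onset and duration". SAP 1.6 (i) lists time to onset and duration among the adverse event endpoints. It defines the collection window as "the period from the signing of a study specific informed consent to study exit for a subject", so collection begins before dosing.

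SAP 2.5 places the safety summaries on Observed Cases, with no inferential tests; Protocol 9.1.2.4 also uses Observed Cases for safety. SAP 2.1.2 summarises quantitative variables by mean, SD, median, quartiles, minimum and maximum.

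**The concern.** Assuming that an event of unknown start began at treatment is a familiar cautious convention when the question is whether to count the event. It is not cautious when the assumed date is then used as data to calculate how soon an event appeared and how long it lasted. Onset becomes the earliest possible post-dose value, and duration becomes the longest one compatible with a post-dose start.

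The SAP is also uneven. Without a stop date, duration is treated as unknown. Without a start date it is just as unknown, yet a number is produced. SAP 2.4.1 describes Observed Cases as involving no imputation, and the treatment-day rule departs from that principle.

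What is at stake is the description of tolerability. The two endpoints are tabulated by treatment group, SOC and PT, with about 80 subjects per dose, so cells may hold few events. One artificial value can then become the reported maximum and pull the mean.

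**Working it through.** The documents give no figure to reproduce, so the check applies the SAP's own formulas.

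**Inputs**
- Time to onset = start − treatment date (SAP 2.5.2).
- Duration = stop − start + 1 (SAP 2.5.2).
- A missing start is set to the treatment date; a missing stop gives no duration (SAP 2.5.2).
- The latest visit named in the visible text is Month 9/early termination (Protocol 7.3.2), so a true onset around Day 180 is possible.
- The number of missing start dates is not given. The counts below are assumptions.

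**Single event.** Let treatment be Day 0, the true start Day s and the stop Day e.
- Onset: the true value is s; the rule gives 0.
- Duration: the true value is e − s + 1; the rule gives e − 0 + 1 = e + 1. The difference is (e + 1) − (e − s + 1) = s.

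Duration is therefore overstated by exactly the true onset day. For a 7-day event, e = s + 6:

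| True onset (day) | Stop (day) | True duration | Onset by the rule | Duration by the rule | Excess |
|---|---|---|---|---|---|
| 14 | 20 | 7 | 0 | 21 | 14 |
| 30 | 36 | 7 | 0 | 37 | 30 |
| 90 | 96 | 7 | 0 | 97 | 90 |
| 180 | 186 | 7 | 0 | 187 | 180 |

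If the stop date is also missing, only onset is affected.

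**Effect on a mean.** If m of n related events have a missing start, a recorded stop and true onset on Day s, mean duration rises by m × s / n.
- 2 of 40, Day 14: 2 × 14 / 40 = 0.7 day.
- 2 of 40, Day 180: 2 × 180 / 40 = 9 days.
- 1 of 20 seven-day events, Day 180: (19 × 7 + 187) / 20 = 16.0 days, against 7.0.
- 1 of 50 seven-day events, Day 180: (49 × 7 + 187) / 50 = 10.6 days, against 7.0.

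In each case mean time to onset falls by the same m × s / n.

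**Stop date before dosing.** The rule gives e + 1: a stop on Day −1 gives 0, on Day −2 gives −1, on Day −5 gives −4. A stop on Day 0 or later always gives at least 1. Zero or negative values therefore need a recorded stop date earlier than treatment.

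**The case against.** The strongest reply is that this will hardly ever happen and will change little when it does. Protocol 7.2.6.2.1 requires the onset date for every adverse event and has subjects asked about changes at each visit. Protocol 10.3 has data clarifications resolved before lock. Overstated duration needs an unknown start together with a known stop. The summaries are descriptive, medians and quartiles resist a single outlier except in very small cells, and the listings of eCRF and derived data under SAP 2.1.2 would let a reader spot an imputed start. All of this stands. It limits the size of the problem but does not make the derived values right.

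Three stronger readings are tempting, and the documents do not support them.

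- *Negative durations will appear in the tables.* The summaries cover treatment-related events only. Under Protocol 7.2.6.1.7, relatedness needs a Yes to possible causation by the product or its injection. An event that ended before the injection should not receive one. Such values would normally stay in derived data and listings, and would reach a table only through a wrong causality entry.
- *Events that ended before dosing become treatment-emergent.* The imputation sentence appears only with the onset and duration derivations. SAP 1.6 (i) defines TEAE status by onset time relative to dosing and does not mention an imputed date. Whether the assumption carries over is not stated.
- *A known month or year is ignored.* SAP 2.5.2 speaks of a missing date and does not say that a partial date counts as missing. SAP 2.1.3 on data transformations is redacted and could hold a partial-date rule.

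**Conclusion.** The point holds for treatment-related events whose start date is missing. By the SAP's own formulas, time to onset is then 0 whatever the true day and, if a stop date exists, duration is too long by the true onset day. That part is certain.

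The aggregate effect is not known and is probably small. The range of 0.7 to 9 days on mean duration rests on an assumed 2 affected events in 40, with true onset on Day 14 or Day 180. On the visible text, no efficacy result and no incidence count is affected. This is a minor improvement to two listed descriptive endpoints, worth making because it is nearly free and removes an inconsistency within one SAP subsection.

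**What to change.** In SAP 2.5.2, treat a missing start as the SAP already treats a missing stop: leave time to onset and duration missing for adverse events with a fully missing start date, and report the number of such events by treatment group beside the onset and duration summaries.

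State also whether the treatment-day assumption is used for TEAE status. If it is, do not apply it when the recorded stop date is before dosing.

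The cost is two or three sentences and minor programming. The downside is slightly fewer events in the onset and duration tables, which the reported count makes visible.

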### 2.5.3 Other Safety Assessments

Data for hematology, blood chemistry, [REDACTED] and vital signs will be summarized by treatment group using descriptive statistics with the value at each visit as well as the change from baseline. The numbers and percentages of subjects with abnormalities in focused physical examination will also be summarized by treatment group. The results of the urine pregnancy tests will only be listed.

## 2.6 Data Safety Monitoring Committee Reviews

There will be two reviews by an unblinded independent Data Safety Monitoring Committee (DSMC) during the study. [REDACTED]

[REDACTED]

[REDACTED]

[REDACTED]

[REDACTED]

### 2.6.1 Pre-Specified Stopping Criteria

The DSMC reviews will be based on tables of summary statistics and listings. No statistical inference will be performed.

Evaluation of safety data will include application of the following stopping criteria:

- [REDACTED]
- [REDACTED]
- [REDACTED]

Further, the DSMC will review the list of AEs (including confirmed AEs of local or remote spread of toxin) and advise the Sponsor of safety findings that may result in discontinuation of study enrollment.

## 2.7 Interim Analyses

[REDACTED]

[REDACTED]

[REDACTED]

[REDACTED]

[REDACTED]

[REDACTED]

## 2.8 Determination of Sample Size

[REDACTED]

[REDACTED]

[REDACTED]

[REDACTED]

Thus, a sample size of 80 in each group is planned to be sufficient to explore the safety and responder rates over time.

[REDACTED]

[REDACTED]

